1. BACKGROUND AND RATIONALE

A substantial contributor to social inequalities in health is diet [1], [2]. The diet of people of lower socioeconomic position (SEP) is more likely to consist of foods of lower nutritional value [3], [4] and this may also result in passive overconsumption because portion sizes of these types of foods have grown in recent times [5], [6].

Offering larger portions compared to small portions increases energy intake. There is robust and reliable evidence of this phenomenon, also known as the ‘portion size effect’ (PSE) [7], [8]. It is unclear who is most susceptible to the PSE [9]. A recent online trial showed that the PSE on intended consumption of unhealthy snacks was 18-24% larger for participants of lower SEP compared to participants of higher SEP [10]. However, to our knowledge, no laboratory study has yet investigated whether people of lower SEP are more susceptible to the influence of portion size on eating behaviour than people of higher SEP.

There is emerging evidence that lower SEP is associated with increased energy intake [11], [12] and/or inadequate energy compensation [13] but little is known about whether lower SEP is associated with a greater susceptibility to external influences on eating like portion size and about the potential mechanisms that could lead disadvantaged people to overeat in response to external influences like portion size. If lower SEP is associated with a greater susceptibility to the PSE then potential explanations include higher impulsivity, lower response inhibition, and larger portion size norms in people of lower vs. higher SEP [14-16]. Serving larger portions (compared to smaller portions) has also been shown to lead to a more pronounced increase in energy intake among participants with lower satiety responsiveness [17]. In addition, people of lower SEP might not compensate for increased energy intake because a positive energy balance is an ‘insurance’ in response to threatened food supply that is associated with lower SEP [18], [19] because their life history (e.g., exposure to harshness and unpredictability during childhood) promotes eating in the absence of hunger or energy need [20], [21]. A tendency to clear one’s plate has been investigated as a potential moderator of the PSE in a small number of studies [41-43], and those with lower SEP may be more likely to clear their plate despite an absence of hunger to avoid food waste (with food waste a higher priority for those with lower income, e.g. [44]). Higher SEP individuals may have stronger health motivation than lower SEP individuals [45,56]. This may reduce the impact of portion size on food intake because individuals with strong health motivation may be concerned about how much they are eating (and avoid overeating when served larger portions). Finally, a tendency to endorse compensatory health beliefs – the belief that energy in the form of calories can be compensated for by restricting or increasing energy intake or expenditure over the course of the day – may be associated with the likelihood of compensating for low calorie meals [46]. To our knowledge no study has investigated compensatory health beliefs as a potential moderator of the PSE.

From a public health perspective, investigating how people of lower SEP respond when exposed to smaller vs. larger portions of foods is of interest because there is a need for equitable interventions that influence dietary behaviour in a way that reduces health inequalities [22], [23]. If people of lower SEP are more prone to being influenced by the external or ‘structural’ aspects of their food environment [15], [24] then reducing portion sizes of commercially provided food may be of particular benefit to lower SEP populations and therefore narrow SEP-based inequalities in diet.

2. OBJECTIVES, OUTCOMES MEASURES AND HYPOTHESES

OBJECTIVES	OUTCOME MEASURES	HYPOTHESES
Primary objective To examine the impact of portion size on energy intake among participants of lower vs. higher SEP.	Energy intake (kcal)	Total energy consumption will be higher from larger compared to smaller portions (PSE). The PSE will be larger in participants of lower vs. higher SEP.
Secondary objectives To examine the reasons why the PSE may vary based on participants' SEP. If no relationship exists, we will examine whether the individual difference measures moderate the PSE	Impulsivity Inhibition Portion size appropriateness Satiety responsiveness Plate clearing tendencies Perceived food insecurity Resource availability in childhood Food choice motives Compensatory health beliefs	The relationship between SEP and PSE may be mediated by individual difference measures.

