(*Level 6: degree apprenticeship; degree with honours – for example bachelor of the arts (BA) honours, bachelor of science (BSc) honours; graduate certificate; graduate diploma; level 6 award; level 6 certificate; level 6 diploma; level 6 NVQ; ordinary degree without honours*)
 - Master's degree or equivalent
(*Level 7: integrated master's degree, for example master of engineering (Meng); level 7 award; level 7 certificate; level 7 diploma; level 7 NVQ; master's degree, for example master of arts (MA), master of science (MSc); postgraduate certificate; postgraduate certificate in education (PGCE); postgraduate diploma*)
 - Doctorate or equivalent
(*Level 8: doctorate, for example doctor of philosophy (PhD or Dphil); level 8 award; level 8 certificate; level 8 diploma*)

We will also aim to stratify recruitment by age (50% 18–25 years; 50% 26+ years), with equal proportions of each age group in each education group (lower, higher).

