4.2. Inclusion criteria

- Female only
- UK residents, age ≥ 18
- BMI between 22.5 and 32.5 kg/m²; as approximately 70% of adults in England have a BMI within this range [25]
- Proficiency in English language
- Self-report liking each of the test foods

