RANDOMISATION	
 ▪ Participants will be randomly assigned to receive the larger portion sizes at the first experimental session and the smaller portion sizes at the second experimental session or vice versa. ▪ A randomisation sequence will be created using Random Allocation Software [35] with a 1:1 allocation stratified by highest educational qualification (Group 1: low ≤ A level, 18-25 years; Group 2: low ≤ A level, 26+ years, Group 3: ≥ degree, 18-25 years, Group 4: ≥ degree, 26+ years). ▪ The allocations will be placed inside envelopes for each group; the envelopes will be sequentially opened each time a participant from one group consent to take part in the study. ▪ Participants' two experimental sessions should take place on the same day of the week
STUDY DAY 1	
 ▪ Remind allowed food / drink, physical activity restriction and install the FitBit ▪ Sleep, mood, and hunger ratings ▪ Breakfast 30 minute session between 7 am and 10:30 am ▪ Snack box 
 ○ Provide the snack box after breakfast ▪ Lunch 30 minute session (between 12pm and 2pm) ▪ Dinner 30 minute session (between 5pm and 7pm – at least 4 hours after lunch) ▪ Organise the following steps: 
 ○ Remind the date of the next session (washout)
WASHOUT SESSION	
 ▪ Participants return FitBit device and snack box ▪ Check if any additional foods/drinks consumed ▪ Remind participants about date of next session (Study Day 2)

STUDY DAY 2	
 ▪ Remind allowed food / drink, physical activity restriction and install the FitBit ▪ Sleep, mood, and hunger ratings ▪ Breakfast 30 minute session between 7 am and 10:30 am ▪ Snack box 
 ○ Provide the snack box after breakfast ▪ Lunch 30 minute session (between 12pm and 2pm) ▪ Dinner 30 minute session (between 5pm and 7pm – at least 4 hours after lunch) ▪ Organise the following steps: 
 ○ Remind the date of the next session (final session)

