7.4.2. Sensitivity analyses

Sensitivity analyses will be conducted to examine whether the pattern of results from the main analyses differ after 1/ excluding participants guessing the aims of the study, 2/ excluding outliers on main outcome variables (identified as those with a value $>$ 3SD from condition mean) and influential cases (identified as those with a Cook's distance $>$ 1, indicating a multivariate outlier [37], 3/

substituting SEP measure (highest educational qualification, \leq A level, $>$ A level) with alternative measures of SEP (level of education – composite score, subjective socioeconomic status (1-10), and household income).

The main analyses will also be repeated controlling for any non-SEP based demographic variables (e.g. BMI, age) that significantly differ between the higher vs. lower SEP groups in order to examine if results remain consistent. To examine whether the order that portions are presented impacts the findings, the main analyses will be repeated with an additional 2-level between-subjects factor (portion size order: smaller, larger vs larger, smaller). Finally, the main analyses will be repeated with dishware size as an additional 2-level within-subjects factor (dishware size: smaller vs larger).

We will report whether sensitivity analyses result in deviations from the pattern of significance to the main analyses (i.e., any significant differences between conditions becoming not significant, and vice versa).

Note if $>30\%$ participants guess the study aim we will include aim guessing as a between-subjects factor in ANOVA rather than use listwise removal.

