7.5. Secondary analyses

7.5.1. Mediation analyses

For each participant, we will compute the average daily energy intake in the larger portion condition minus average daily energy intake in the smaller portion size condition, referred below as the portion size effect (PSE).

We will first report and compare the individual measures of impulsivity, inhibition, portion size appropriateness, satiety responsiveness, plate clearing tendencies, perceived food insecurity, resource availability in childhood, food choice motives, and compensatory health beliefs for lower and higher SEP groups using means, standard deviations and T-tests. If we find individual differences for any of these measures between participants of lower and higher SEP, mediation analyses will be performed in order to examine the extent to which it mediates the effect of SEP on the PSE (**Figure 2**).

[figure not shown]

Figure 2. Mediation diagrams for the PSE. Indirect effect of SEP on the PSE through a mediator M = $c - c' = ab$.

The mediation will be tested by estimating the indirect effects of SEP on the PSE through all the potential mediators and testing their indirect effect using bias-corrected bootstrap. We will use the PROCESS macro (Model 4 – one mediator at a time and all together) in SPSS that provides asymmetric bias-corrected bootstrap confidence intervals for inference about the indirect effects using 5,000 bootstrap samples [38]. Mediation will be tested by determining whether or not the confidence intervals of the indirect effects estimates contain zero.

If we do not find evidence that the PSE is moderated by SEP or that our individual difference measures do not explain moderation by SEP, we will repeat the primary analysis replacing SEP with the individual measures, to examine whether any of the individual difference measures moderates the main effect of portion size on daily energy intake.

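### The mediation models in section 7.5.1 have no covariates, so if age is related to a mediator and also modifies the portion response, part of that association could be reported as mediation

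*Combined protocol and SAP*

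**What the plan says.** Section 2 makes it a secondary objective to explain variation in the portion size effect (PSE) by socioeconomic position (SEP), and hypothesises: "The relationship between SEP and PSE may be mediated by individual difference measures". Section 7.5.1 carries this out. The PSE is each participant's daily intake in the larger condition minus that in the smaller one. Measures enter through a gate: "If we find individual differences for any of these measures between participants of lower and higher SEP, mediation analyses will be performed". The model is given as "We will use the PROCESS macro (Model 4 – one mediator at a time and all together) in SPSS", and the decision rule as "Mediation will be tested by determining whether or not the confidence intervals of the indirect effects estimates contain zero". No covariate is named in either equation, and no interval level is stated.

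The randomised element is order: "Participants will be randomly assigned to receive the larger portion sizes at the first experimental session and the smaller portion sizes" second, or the reverse (section 6). SEP is observed education, and the mediators are questionnaire, task or portion-selection scores.

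On age, section 4.2 requires "UK residents, age ≥ 18" and sets no upper limit. Section 4.1 aims for two age bands, 18–25 and 26+, "with equal proportions of each age group in each education group (lower, higher"). Section 7.4.2 states: "The main analyses will also be repeated controlling for any non-SEP based demographic variables (e.g. BMI, age"), and restricts this to variables that differ significantly between the SEP groups.

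**The concern.** An indirect effect is the product of the SEP-to-mediator path (a) and the mediator-to-PSE path (b). Path b is observational, so any common cause of mediator and PSE biases it, even when that cause is perfectly balanced across SEP. Age is an obvious candidate: its range is open-ended, and the plan itself names it as a possible covariate elsewhere.

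The plan's safeguards act on other paths. The age quotas guard path a against age imbalance, but within each education group age can still vary with both mediator and PSE. Extending the 7.4.2 rule to the mediation models would not help much, because it selects covariates by SEP difference and the quotas are meant to remove that difference for age. The joint model adjusts the mediators for one another, not for age. The gate favours measures with a non-zero path a, which turns a spurious path b into a spurious indirect effect.

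At stake is the explanation offered for an SEP difference: a measure with no effect of its own on the PSE could be named as the reason for it.

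**Working it through.** **1. The plan's own figure.** Section 7.6 gives f = 0.175, within-subject correlation 0.7, 85% power and N = 46. With λ = N × 2 × f² / (1 − ρ) = 46 × 2 × 0.030625 / 0.3 = 9.39 and df = 1 and 44, power for the portion size × SEP interaction is 85.02%. At N = 60 it is 93.1%. N = 46 is reproduced.

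**2. A yardstick for r.** On the PSE difference score with two equal groups, λ = N d² / 4. So d = √(4 × 9.39 / 46) = 0.90, and r = d / √(d² + 4) = 0.90 / √4.82 = 0.41. This is the SEP effect that the trial is powered to detect.

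**3. What age must do.** If age adds the same amount to intake on both days, it cancels in larger minus smaller. Age confounds path b only if it changes the response to portion size.

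**4. Size of the bias.** Assumptions, none of them given in the documents: SEP groups differ by 0.8 SD on the mediator, the true path b is zero, age is independent of SEP, and age correlates r with both mediator and PSE within SEP group. With unit variances, the fitted b is then r × r, and the spurious indirect effect is 0.8 r² SD of the PSE: 0.072 at r = 0.3, 0.128 at 0.4 and 0.200 at 0.5. Simulated means at N = 60 were 0.066 (r = 0.3) and 0.191 (r = 0.5), and about 0 with age as a covariate.

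**5. False-mediation rate.** Simulation of 1,500 trials per setting with 600 bootstrap samples (the plan uses 5,000), a t-test gate at p<0.05 and a 95% bias-corrected interval. Rates are among trials that pass the gate.

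| r | No covariate, N=46 | No covariate, N=60 |
|---|---|---|
| 0 | 11% | 11% |
| 0.3 | 14% | 17% |
| 0.4 | 27% | 29% |
| 0.5 | 48% | 60% |

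A repeat with 500 trials per setting gave, without/with age:
- N=46: 15%/7%, 29%/10% and 48%/12% at r = 0.3, 0.4 and 0.5.
- N=60: 17%/10%, 30%/9% and 56%/8%.

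With age adjusted, the rate is roughly 7–12% throughout.

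**6. Sensitivity to thresholds.** Section 7 sets p<0.01 for secondary analyses. If that is read as a p<0.01 gate and a 99% interval (an assumption), N = 60 gives about 13% without age against 3.5% with it at r = 0.4, and 33% against 2% at r = 0.5. At r = 0.3 the unadjusted rate is 4.9%/6.6% at N=46/60. With a percentile 95% interval and the p<0.05 gate, r = 0.4 gives 18%/22% against 6% adjusted.

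**7. Cost of adjusting.** In 4,000 simulations with two irrelevant covariates and b = 0.39, b-path power fell from 71% to 69% at N = 46 and from 82% to 80% at N = 60.

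**The case against.** The strongest reply is that nothing in the documents shows age modifying the PSE. The background in section 1 lists many candidate drivers of the PSE, and age is not among them. A reader might infer that it is enough for older and younger women to eat different amounts. It is not, for the reason in step 3. By the yardstick in step 2, r = 0.4 makes age about as strong a modifier as the SEP effect the trial is powered for, and r = 0.5 makes it stronger; the mediator must correlate with age as strongly. At r = 0.3 the excess over r = 0 is only 3 points at N=46 (14 − 11) and 6 at N=60 (17 − 11). At r = 0.2 the rate was 9–10%, indistinguishable from no confounding. All of this stands, and it limits the size of the point. It does not supply protection for path b.

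A reader might also read the whole of each unadjusted rate as confounding. About 11% is present at r = 0 and comes from the bias-corrected interval in small samples; age adjustment does not remove it.

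Finally, the fallback analyses in 7.5.1 also lack covariates, and one might infer that they are biased too. They ask only whether the PSE differs across levels of a measure, which is effect modification and needs no causal reading. The same confounding matters there only if a measure is then interpreted as a cause of the PSE difference.

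**Conclusion.** The gap is real but conditional. Section 7.5.1 leaves path b open to confounding by age, and no other provision closes it. The documents do not support saying that age will produce a false mediator, only that it could. That requires a measure that differs by SEP, an association of age with that measure, and modification of the portion response by age. The excess false-mediation rate is a few points at r = 0.3 and becomes large only at r = 0.4–0.5. All rates rest on the assumed 0.8 SD difference, equal correlations and the chosen gate and interval level; stricter thresholds lower them.

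The finding concerns a secondary analysis. The portion size × SEP test and its sample size are untouched. Nor would age adjustment make the indirect effects causal, since it removes one common cause and SEP and the mediators remain observational.

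**What to change.** In 7.5.1:
- Pre-specify age in years as a covariate in both the mediator and the PSE equation of every Model 4 run, single and joint, whether or not age differs by SEP. Base the mediation statement on that interval.
- Report a further run that adds BMI, labelled as a sensitivity analysis because BMI may lie on the causal path.
- Describe the indirect effects as associational.
- In the fallback moderation analyses, add portion size × age only where a measure will be interpreted as a cause of the PSE difference.

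The cost is SAP wording and the 1–2 points of b-path power shown in step 7. Age is already collected, BMI follows from height and weight at screening, and PROCESS accepts covariates.

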3. EXPERIMENTAL DESIGN

Participants will be randomised into a cross-over design with two study days corresponding to two conditions: larger portion size condition or smaller portion size condition. Each study day will last one day and be separated by a minimum 1-week and maximum 6-week washout period. The two study days will be scheduled for the same day each week. On both days, participants will be served all meals *ad libitum* in the lab (including breakfast and second helpings) and will be provided with snacks to consume outside of the lab – but only the size of the initial portion of the main meal provided for lunch and dinner will be manipulated. Energy intake from all meals and snacks will be recorded.

4. PARTICIPANTS AND RECRUITMENT

4.1. Recruitment

Recruitment advertisements will be placed on social media (Facebook, Instagram, Twitter), online noticeboards (Gumtree, Call for Participants), and University of Liverpool (and other local universities') staff and students announcements and mailing lists. Flyers and posters will be distributed around the University of Liverpool campus, and if needed in local businesses and via letterbox drops in local residences with a particular focus on the most deprived areas based on the Index of Multiple Deprivation (IMD). Participants will be reimbursed for their time and expenses (£70 at the end of the study).

Recruitment will be stratified by highest educational qualification achieved or currently studying for as follows:

- 50% lower qualification levels

- No formal qualifications
- 1–3 GCSEs or equivalent
(*Level 1: first certificate; GCSE – grades 3, 2, 1 or grades D, E, F, G; level 1 award; level 1 certificate; level 1 diploma; level 1 ESOL; level 1 essential skills; level 1 functional skills; level 1 national vocational qualification (NVQ); music grades 1, 2 and 3*)
- 4+ GCSEs or equivalent
(*Level 2: CSE – grade 1; GCSE – grades 9, 8, 7, 6, 5, 4 or grades A*, A, B, C; intermediate apprenticeship; level 2 award; level 2 certificate; level 2 diploma; level 2 ESOL; level 2 essential skills; level 2 functional skills; level 2 national certificate; level 2 national diploma, level 2 NVQ; music grades 4 and 5; O level – grade A, B or C*)
- A level or equivalent
(*Level 3: A level; access to higher education diploma; advanced apprenticeship; applied general; AS level; international Baccalaureate diploma; level 3 award; level 3 certificate; level 3 diploma; level 3 ESOL; level 3 national certificate; level 3 national diploma; level 3 NVQ; music grades 6, 7 and 8; tech level*)
- 50% higher qualification levels
 - Certificate of higher education (CertHE) or equivalent
(*Level 4: certificate of higher education (CertHE); higher apprenticeship; higher national certificate (HNC); level 4 award; level 4 certificate; level 4 diploma; level 4 NVQ*)
 - Diploma of higher education (DipHE) or equivalent
(*Level 5: diploma of higher education (DipHE); foundation degree; higher national diploma (HND); level 5 award; level 5 certificate; level 5 diploma; level 5 NVQ*)
 - Bachelor or equivalent
(*Level 6: degree apprenticeship; degree with honours – for example bachelor of the arts (BA) honours, bachelor of science (BSc) honours; graduate certificate; graduate diploma; level 6 award; level 6 certificate; level 6 diploma; level 6 NVQ; ordinary degree without honours*)
 - Master's degree or equivalent
(*Level 7: integrated master's degree, for example master of engineering (Meng); level 7 award; level 7 certificate; level 7 diploma; level 7 NVQ; master's degree, for example master of arts (MA), master of science (MSc); postgraduate certificate; postgraduate certificate in education (PGCE); postgraduate diploma*)
 - Doctorate or equivalent
(*Level 8: doctorate, for example doctor of philosophy (PhD or Dphil); level 8 award; level 8 certificate; level 8 diploma*)

We will also aim to stratify recruitment by age (50% 18–25 years; 50% 26+ years), with equal proportions of each age group in each education group (lower, higher).

4.2. Inclusion criteria

- Female only
- UK residents, age ≥ 18
- BMI between 22.5 and 32.5 kg/m²; as approximately 70% of adults in England have a BMI within this range [25]
- Proficiency in English language
- Self-report liking each of the test foods

